4.10 Scales & Forms

We will offer clinical interviews and study forms in Spanish. All scales will explore the last 7 days, except M.I.N.I (lifetime), TSRQ (study duration).

- **(M.I.N.I.)** - The M.I.N.I. is a brief structured diagnostic interview, developed jointly by psychiatrists and clinicians in the United States and Europe, for DSM and ICD psychiatric disorders. With an administration time of approximately 15 minutes, it is designed to meet the need for a short but accurate structured psychiatric interview for clinical trials. According to researchers in the Division of Clinical and Treatment Research at the National Institute of Mental Health (NIMH), the M.I.N.I. is a fully validated and more time-efficient alternative to the Structured Clinical Interview for DSM Disorders (SCID) (Sheehan et al., 1998). Validated in Spanish (Ferrando L. et. al, 1998).
- **Systematic Assessment for the Treatment of Emergent Events (SAFTEE-SI)** - The SAFTEE is a commonly used instrument originally developed by NIMH and adapted into a self-report instrument. The version of the scale we plan to use is the same

Transcranial Near Infrared Laser Therapy in Subjects with Major Depressive Disorder: A Laser Dosing Study.

used by the NIMH-sponsored CO-MED multicenter trial, and systematically examines all potential treatment-emergent side effects and discusses specific adverse symptoms, including suicidal thoughts and behaviors, and self-injurious behavior.

- **Hamilton Depression Rating Scale - 17 items (HAM-D-17)**; Hamilton, 1960
 - The doctor completes this instrument based on his or her assessment of the patient's depressive symptoms, using a structured interview and defined anchor items. The goal of the HAM-D is to quantify the degree of depression in patients who already have a diagnosis of major depression. Questions focus on neurovegetative and other depressive symptoms experienced in the past 7 days. There are several different versions of the HAM-D; they differ only in the number of questions included. The standard form generally used in research studies is the 17-item Hamilton D (HAM-D-17). Responses to the questions are scored on a scale of 0-4 or 0-2, with higher scores indicating more severe pathology. Scores on the HAM-D-17 generally fall into the following ranges: a) not depressed = 0-7; b) mildly depressed = 8-13; c) moderately depressed = 14-18; d) severely depressed = 19-22; e) very severely depressed = 23 or more. Validated in Spanish by Ramos-Brieva (1986).
- **Quick Inventory of Depressive Symptomatology: Clinician-Rated Scale (QIDS-C)** - This is a brief (16-item) clinician-rated inventory of core depressive symptoms such as sleep, depressed mood, appetite, concentration, suicidal ideation, interest, energy, psychomotor retardation, or agitation. Validated in Spanish by Planas et al. (2014).
- **Clinical Global Impressions: Severity and Improvement (CGI-S, CGI-I)** - The clinician scores these two instruments from 1 to 7 based on the assessment of the subject's overall clinical status. Measured based on history and scores on other instruments: (a) depressive severity (CGI-S) and (b) clinical improvement (CGI-I). Validated in Spanish by García-Portilla (2011).
- **Anxiety Symptom Questionnaire (ASQ)** - This is a 17-item self-report questionnaire, used in Spanish, that measures the frequency and intensity of 17 anxiety symptoms, including nervousness, worry, irritability, trouble relaxing, insomnia, lack of energy, difficulty concentrating, somatic symptoms, and impaired functioning due to anxiety.
- **Symptoms of Depression Questionnaire (SDQ)** - This is a comprehensive measure of depression that includes assessment of symptoms on the anxiety-depression spectrum. It assesses irritability, anger outbursts, and anxiety symptoms along with symptoms commonly considered to be symptoms of depression. Factor structure analysis of the SDQ identified 5 subscales, including one on the anxiety-depression spectrum, with adequate internal consistency and concurrent validity in Spanish (Pedrelli et al., 2014).
- **Columbia Suicide Severity Rating Scale (C-SSRS)** For suicidal ideation and behavior: an FDA-endorsed instrument for clinical trials. This instrument systematically tracks suicidal ideation and behavior (e.g., suicide attempts, desire to die, suicidal thoughts, plan and intent) (Posner et al. 2007) Validated in Spanish by Al-Halabí et al.(2016).
- **Adverse Event Form**- The adverse event form captures any adverse events (serious or otherwise) specifically related to the application of TLT. This form will help determine if the side effects of TLT are too great for a participant to continue in the study.
- **Concomitant Medication Form** - This form will be completed at each TLT study visit, including the screening visit, as a safety monitoring tool.

Transcranial Near Infrared Laser Therapy in Subjects with Major Depressive Disorder: A Laser Dosing Study.

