Study Design:	
Multi-center, randomized, sham, double-blind.
 
This trial will randomize 112 subjects into 4 equal groups: bilateral continuous wave (BCW), bilateral pulsed wave (BPW 1-2) and SHAM. All subjects, investigators (except the study statistician) and outcome assessors will be blinded to group assignments. The device operator will be aware of group assignments.
 
All subjects will receive 3 NIR-TLT sessions per week for 6 weeks. A follow-up evaluation will be performed 2 weeks after the end of the study. The treatment will follow these specifications: wavelength 830 nm; average irradiance 54.8 mW / cm²; average fluence of 65.8 J / cm² (according to the parameters used in the ELATED-2 study at MGH with the Omnilux New U device), being the total fluence delivered: 3.6 kJ (bilateral) or 1.8 kJ (unilateral), either on the subject's forehead, at or near the electroencephalography (EEG) sites F3 and F4.
 
All NIR-TLT sessions will be 429 seconds (7.15 minutes), regardless of group assignment.

Study population:	
Patients eligible to participate in the study will be diagnosed with MDD by DSM criteria (MINI). Subjects will be between 18 and 75 years of age (not yet 76 years of age) on the date of the examination.

Duration of participation:	
Research subjects will remain in the study for 8 weeks. (6-week treatment period, plus 2-week follow-up). The total duration of the study will be 24 months.

Near Infrared Transcranial Laser Therapy in Subjects with Major Depressive Disorder: A study of Dosing with Laser.

Criteria for valuation:

- **Main:** Improvement of depressive symptoms from each of the four doses of NIR-TLT. Assessed using HAMD-17, at 3 time points (visit 1, visit 9 and visit 18).
- **Secondary:** Safety and tolerability. Assessed by SAFTEE- SI (self-assessed), and collection of serious adverse events throughout the study. Safety data will be used to assess the tolerability of each of the NIR-TLT doses.
Changes in brain electrophysiology (electrical activity): Commercially available EEG devices will be used to collect data on brain electrical activity. At 3 time points (visit 1, visit 9 and visit 18).
- Changes in measurements of MDD symptom severity assessment scales:
 - Doctor Administered Scales: QIDS-C and CGI-S
 - Patient-reported scales: ASQ and SDQ

Entry Criteria:

Inclusion Criteria

1. The age of the subjects in the examination will be between 18 and 75 years (inclusive).

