4.4 Study Design

This study is a multicenter, randomized, sham-controlled, double-blind study on the use of transcranial continuous light therapy as a treatment for depressive symptoms in patients with major depressive disorder (MDD). Laser light therapy is tested in a strict parallel design.

This study will include 112 subjects randomly assigned to each of the four NIR-TLT treatment groups (28 subjects/group).

All subjects will receive three NIR-TLT treatments per week for 6 weeks and will complete a follow-up evaluation two weeks after treatment completion. All subjects and investigators (except the study statistician) will be blinded to treatment sequence assignment.

Energy will be administered at a wavelength of 808 nm, bilaterally to two frontal areas on the left and right side of the forehead, at or near electroencephalography sites F3 and F4. To maintain blinding, the treatment duration will be 429 seconds (7.15 minutes) for all groups. The treatment exposure (time during which the laser is active for the duration of the treatment) will be specific for each group, controlled by the device to normalize the treatment fluence of each active session per treatment location. Treatment will follow these specifications: wavelength 830 nm; average irradiance 350 mW / cm²; average fluence of 65.8 J / cm² (according to the parameters used in the ELATED-2 study at MGH with the Omnilux New U device) being the total fluence delivered: 3.6 kJ (bilateral) or 1.8 kJ (unilateral), either on the subject's forehead, at or near electroencephalography (EEG) sites F3 and F4.

The entire session (which includes the 429-second treatment and all procedures described in the "Study Visits" section) is estimated to take 30 minutes or less (Schiffer et al., 2009) (Lampl et al., 2007, Zivin et al., 2009). Additional time is needed to prepare the subject, fit the necessary protections (e.g., goggles), inspect the subject's skin, set up the NIR-TLT devices, and give the subject time to rest after irradiation. NIR-TLT treatment will only be administered by trained personnel who are on study staff. All personnel administering the treatment must pass laser safety training created by the American Institute for Medical Laser Applications and approved by the relevant Committees. The duration of irradiation will be decreased if clinically indicated, based on tolerability as needed.

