4.9 Study Visits

The study includes screening tests, treatment and a series of follow-up visits.

4.9.1 Selection Visit - Week 0

Purpose

The purpose of the screening visit will be to determine the eligibility of patients to participate in the study.

Procedures

Study personnel will consent subjects to the study, perform a psychiatric evaluation, and screen for the presence of MDD using the MINI, QIDS-C, and CGI-S scales.

Laboratory tests (including urine collection for urine biochemical analysis and urine toxin analysis (also called Urine Drug Screen), urine pregnancy test, and a complete physical examination including vital signs and weight will be performed.

Approximately 15 cc \pm 5 cc (15 ml) of blood will be drawn for laboratory safety testing. To confirm that a patient is healthy enough to participate, a complete blood work-up with differentials, thyroid stimulating hormone test, blood biochemistry (glucose, calcium, sodium, potassium, carbon dioxide, chlorine, albumin, total protein, alkaline phosphatase, transaminases, total and fractionated bilirubins, urea, creatinine) and a high sensitivity C-reactive protein test will be performed. A PET scan will be performed on patients within the study subgroup to meet the exploratory objective.

Near Infrared Transcranial Laser Therapy in Subjects with Major Depressive Disorder: A study of Dosing with Laser.

Once all tests and procedures are available for review, study personnel will determine subject eligibility based on all inclusion and exclusion criteria.

Subjects who report having taken antidepressants at the screening examination may choose to continue medication during the study or taper and discontinue therapy prior to the baseline visit (under the supervision of a treating doctor). However, subjects who have discontinued more than two antidepressants in the current episode of depression will be excluded.

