Risk of worsening depression, suicidality and manic change: Worsening depression and increased suicidality are possible complications of antidepressant treatments prescribed to subjects with MDD. We will minimize this risk by selecting only subjects who do not exhibit active suicidal ideation at screening. We will also discontinue any subject who develops active suicidal ideation during the course of the study (C-SSRS) and is considered to be in imminent danger; we will then coordinate appropriate levels of care and standard antidepressant treatment (see 4.9 Termination). Manic changes are potential adverse events and will also be closely monitored during antidepressant treatment. Our strict schedule of clinical study visits will allow early recognition of treatment-emergent suicidal ideation or prodromal hypomanic signs. Subjects who develop mania or hypomania will be discontinued and provided with the appropriate level of care.

Answering detailed questionnaires may create a slight degree of inconvenience for subjects.

Duration of testing for cognitive circuitry: The total testing duration takes a total of 40 minutes at baseline and 40 minutes at weeks 5 and 9. There is no expected risk to patients beyond the 40 minutes of sitting at the computer for testing and possible startle experience. Every effort will be made to ensure that patients are comfortable and safe during this period, and the study can be stopped at any time. Beyond these problems, there is little or no risk to patients.

Risk of bruising: venous puncture may cause accidental bruising when blood is drawn from the forearms.

4.20.2 Benefits:

Study subjects will receive a systematic MINI assessment of their DSM comorbidity. This information will be readily available to their treating doctors if subjects so desire and agree to disclose. This information can guide long-term treatment. In the short term, the subject will receive close and systematic depression follow-up and formalized cognitive assessments beyond current standards of care. Easy access to routine physical examinations is also a potential benefit. Subjects will have access to a different treatment modality if counseling and/or medications were not sufficient or not acceptable to them. The treatment itself with transcranial laser therapy (TLT) can potentially alleviate depressive symptoms on a level equal to antidepressant medication.

4.20.3 Allowed and prohibited concomitant interventions:

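### The blanket 7-day look-back in section 4.10 leaves the first 7 of the 14 off-treatment days outside the C-SSRS, and the protocol contradicts itself on when the C-SSRS is given

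*Protocol*

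**What the plan says.** Section 4.10 opens with a recall rule for all instruments: "All scales will explore the last 7 days, except M.I.N.I (lifetime), TSRQ (study duration"). Two instruments are exempt. One of them, TSRQ, is neither described nor scheduled anywhere else in the protocol.

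The C-SSRS is described later in the same section: "This instrument systematically tracks suicidal ideation and behavior (e.g., suicide attempts, desire to die, suicidal thoughts, plan and intent"). No recall period is given there, and no other section assigns it a lifetime or since-last-visit version.

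On timing, section 4.4 says that subjects "will complete a follow-up evaluation two weeks after treatment completion", and the Summary gives participation as a "6-week treatment period, plus 2-week follow-up".

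The C-SSRS schedule appears in three places that do not agree:
- The Table of Assessments (section 8) marks it at selection, visits 1 to 9, visit 18 and visit 19, and leaves visits 10 to 17 blank.
- Section 4.9.2 lists it among the safety data collected at treatment visits.
- Section 4.9.3 does not list it among the safety data of the week 8 visit.

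Section 4.20.1 relies on the schedule for detection: "Our strict schedule of clinical study visits will allow early recognition of treatment-emergent suicidal ideation".

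**The concern.** A fixed 7-day window works when assessments are at most 7 days apart. When they are further apart, the days before the window are not asked about at the later visit, and the earlier visit could not have covered them. Giving the C-SSRS at every planned visit would not cure this, because the window creates the gap.

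The interval after visit 18 exceeds 7 days by design. It is also when the laser has just stopped and contact falls from three visits a week to none until week 8. An episode of ideation or intent that begins and resolves in the first of those two weeks need not appear on the instrument that the protocol uses to track suicidality.

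The interval from selection to visit 1 could raise the same problem. Subjects on antidepressants "may choose to continue medication during the study or taper and discontinue therapy prior to the baseline visit" (section 4.9.1), and no maximum length for that interval is stated.

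**Working it through.** **Inputs**
- Look-back L = 7 days (section 4.10).
- Visit 18 in week 6 and visit 19 in week 8 (Table of Assessments); follow-up two weeks after treatment ends (section 4.4).
- Three sessions a week for 6 weeks (section 4.9.2). For day numbers I assume sessions on days 1, 3 and 5 of each week, with visit 1 on day 1.

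**The plan's own interval.** Week 8 − week 6 = 2 weeks = 14 days, as stated. On the assumed calendar, visit 9 is day 19, visit 18 is day 40 and visit 19 is day 40 + 14 = 54.

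**Formula.** Days not covered = max(0, interval between consecutive C-SSRS assessments − L).

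| Interval | Schedule followed | Length (days) | Not covered by the C-SSRS |
|---|---|---|---|
| Visit 18 to 19 | Table (C-SSRS at visit 19) | 14 | 14 − 7 = 7 (50%) |
| Visit 18 to 19 | Section 4.9.3 (no C-SSRS at week 8) | 14 | 14 (100%) |
| Visit 9 to 18 | Table (blank at visits 10–17) | 40 − 19 = 21 | 21 − 7 = 14 |
| Visit 9 to 18 | Section 4.9.2 (every treatment visit) | at most 3 between visits | 0 |

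The 7 missed days are days 40–46 if the window is the 7 days before the visit, or 41–47 if it includes the visit day. The count is the same.

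**Selection to visit 1, assumed interval s days.** Not covered = max(0, s − 7): 0 for s ≤ 7, 3 for s = 10, 7 for s = 14, 21 for s = 28 and 35 for s = 42. The protocol gives no value for s.

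**Do other scales fill the post-treatment gap?** SAFTEE-SI includes suicidal thoughts and behaviours, and QIDS-C includes suicidal ideation. Both are due at week 8, but both fall under the same 7-day rule, so they look at the same last week. Between visits 9 and 18 the position differs: the Table marks SAFTEE-SI at visits 10 to 17, so self-report continues there even if the C-SSRS does not.

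**The case against.** The strongest reply is that suicidality in the missed week is not lost. Adverse events are recorded from consent to the end of the study (4.17.1), whether or not attributed to the device (4.17.3). An attempt that is life-threatening or leads to hospitalization is a serious adverse event. The adverse event form is due at visit 19, and patients are told to contact the site between visits if symptoms worsen (4.17.2). This stands, and it narrows the point to structured rating, mainly of ideation or intent that has resolved before the window opens. It is not complete cover: 4.10 describes the adverse event form as limited to events related to the treatment, and between-visit contact depends on the patient.

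A second reply is that the opening sentence of 4.10 is generic, apparently carried-over text, since it names a scale the trial does not use. That may be so. It is still the only recall rule given for the C-SSRS, and it is worded as a closed list.

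Three stronger readings are tempting, and the protocol does not support them:
- A reader might infer that a between-group safety comparison loses half its off-treatment period. Section 5 plans no C-SSRS analysis; it compares SAFTEE-SI at visits 1, 9 and 18, and adverse events without a 7-day window.
- A reader might infer that a screening gap is certain. The Table labels selection week 0 and visit 1 week 1; at about one week the gap is zero.
- A reader might add the visit 9 to 18 gap and conclude that 14 + 7 = 21 of 54 days (39%) are missed. Two thirds of that figure comes from the blank Table cell and disappears if 4.9.2 is followed.

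**Conclusion.** The point holds in a limited form. If 4.10 and the Table of Assessments are followed as written, the C-SSRS misses 7 of the 14 off-treatment days, and the other scales with suicidality content miss the same days. If 4.9.3 governs week 8, the C-SSRS misses all 14. The 7-day figure rests on the 14-day interval in section 4.4 and the Table, and on reading the 4.10 rule literally; the assumed session days affect only the day labels.

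The screening gap is conditional on an interval above 7 days, which the protocol neither states nor limits. The on-treatment gap is conditional on the Table overriding 4.9.2.

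What is lost is systematic assessment of ideation and behaviour. Reported events can still be captured, and sample size, error rate, endpoints and planned analyses are unaffected. The change is worth making because the rule is stated, works badly at a foreseeable point, and is easy to correct.

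**What to change.** 1. In section 4.10, exempt the C-SSRS from the 7-day rule. From visit 1 onward it covers the time since the previous C-SSRS, and its look-back at selection is stated separately. Keep 7 days for the efficacy scales.
2. Delete TSRQ from the same sentence.
3. Reconcile sections 4.9.2 and 4.9.3 with the Table of Assessments on when the C-SSRS is given (visits 10 to 17 and week 8). Step 1 has no effect after visit 18 unless a C-SSRS is given at week 8, so the two changes belong together.

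With a C-SSRS at visit 19, the uncovered off-treatment days fall from 7 to 0. For a screening interval of s days, they fall from max(0, s − 7) to 0.

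The cost of steps 1 and 2 is one sentence in 4.10 and the instruction on the form, with no added visit or form. The small downside is longer recall: 14 days at visit 19, and longer at visit 1 if selection was early. Step 3 is an edit to text and Table; whether it changes the number of assessments depends on how the sponsor resolves the conflict.

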4.17 Clinical Adverse Events

4.17.1 Overview and Definitions

All adverse events will be recorded from the time of Informed Consent until completion or completion of the study. The adverse event CRF must be completed and submitted to the IRB, FDA and Pthera LLC as required. Adverse event management regulations and reporting contained in the FDA and ICH Guidelines will be adhered to.

Consideration of adverse events will hereinafter consist of adverse events, serious adverse events, and adverse device effects, including anticipated and unanticipated adverse device effects.

- **Adverse event** is defined as any unfavorable/undesirable clinical event in a clinical investigation of a subject using a device and/or product that does not necessarily have a causal relationship with this treatment. Therefore, an adverse event can be any unfavorable and/or unintended sign, symptom or disease temporally associated with the use of a product or device, whether or not considered related to it. Only abnormal

Transcranial Near Infrared Laser Therapy in Subjects with Major Depressive Disorder: A Laser Dosing Study.

laboratory values that the investigator considers clinically significant will be classified as adverse events.

- **Serious Adverse Event** is defined as any adverse/undesirable experience that results in any of the following outcomes: 1) death; 2) a life-threatening adverse experience; 3) hospitalization or prolongation of existing hospitalization; 4) a permanent/persistent or significant disability/incapacity, or congenital anomaly/birth defect; 5) major medical events that may not be life-threatening, life-threatening, or require hospitalization may be considered a serious adverse experience when, based on appropriate medical judgment, they may endanger the subject and may require medical or surgical intervention to prevent any of the outcomes listed in this definition.
- **Anticipated adverse device effect** is defined as any adverse effect related to the device or procedure, which is identified in the protocol.

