4.17.3 Reporting Procedures for all Adverse Events

After review with the subject by study site personnel, all adverse events occurring during the study, whether or not attributed to the tPBM-2.0 device or TLT procedure, observed by the investigator or reported by the subject, will be documented in the subject's source document and on the appropriate CRF pages. The following attributes should be assigned:

1. Description of the event
2. Start Date
3. Date of resolution (if applicable)
4. Severity
5. Relation to the study set-up and / or procedures
6. Intensity
7. Action(s) taken
8. Resolution

Intensity is defined as a measure of the severity of a reaction, effect or experience. Measures are described as mild, moderate or severe. However, the event itself may be of relatively minor medical importance.

Transcranial Near Infrared Laser Therapy in Subjects with Major Depressive Disorder: A Laser Dosing Study.

The intensity of adverse events is assessed as mild, moderate or severe according to the following index scale:

Mild

The adverse event is transient, does not require treatment and does not interfere with the subject's daily activity.

Moderate

The adverse event introduces a low level of inconvenience or concern for the subject and may interfere with daily activities, but is usually ameliorated by simple therapeutic measures.

Severe

The adverse event disrupts the subject's usual daily activity and requires systematic therapy or other treatment.

If the adverse event is of such intensity in the judgment of the investigator that it warrants withdrawal from the study, the subject should be withdrawn from treatment. The subject should receive appropriate care under medical supervision until the symptoms disappear.

The relationship of an adverse event to the study device or procedure will be graded as follows:

None

The adverse event is not associated with the use of the study device.

Remote

The temporal association is such that the study device is not likely to have had an association with the observed adverse event.

Possible

This causal relationship is assigned when the adverse event:

- a) Follow a reasonable time sequence of device usage, but
- b) It could have been produced by the subject's clinical condition or other methods of therapy administered to the subject.

Likely

This causal relationship is assigned when the adverse event:

- a) Follow a reasonable time sequence of device use;
- b) It decreases when treatment is suspended;

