In addition, the frequency and severity of side effects and adverse events reported for each dose will be compared using a Fisher's exact test. The corrective actions taken by the doctors as well as the clinical judgment on the likelihood of association of the side effect/adverse event with the NIR-TLT dose will also be reported.

D. Findings visualized in the PET scan:

The analysis of the results obtained in the PET will be for exploratory purposes to study the brain metabolism of the participants, before and at the end of the study intervention in the 4 groups. Following the recommendations of Daniel et al. (Daniel, 2012), for the exploratory analysis we will work with a minimum number of 5 participants per group, with a total of 20 participants.

The results obtained in the PET will be presented in a descriptive manner.

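### Section 4.10 limits the Adverse Event Form to events related to the laser, contradicting the all-events rule in 4.17.1 and 4.17.3 and leaving the between-arm event counts open to a bias of uncertain direction

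*Protocol*

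**What the plan says.** The list of scales and forms in section 4.10 describes the form this way: "The adverse event form captures any adverse events (serious or otherwise) specifically related to the application of TLT". It then gives the form a purpose: "This form will help determine if the side effects of TLT are too great for a participant to continue in the study".

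The adverse event sections set a different scope. Section 4.17.1 states: "All adverse events will be recorded from the time of Informed Consent until completion or completion of the study". Its definition of an adverse event covers anything "temporally associated with the use of a product or device, whether or not considered related to it". Section 4.17.3 sends to the source document and the CRF "all adverse events occurring during the study, whether or not attributed to the tPBM-2.0 device or TLT procedure", and then lists relationship among the attributes to be assigned. The relationship scale begins with the grade None, for events not associated with the device.

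The analysis sections contain no restriction by relationship. Section 5.5 C says that "adverse events reported for each dose will be compared using a Fisher's exact test", and reports the clinical judgement on association separately. Section 5.6 presents the number and percentage of adverse events for each treatment group.

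The Adverse Event Form is the only dedicated adverse event form that the protocol names. It is listed for the exit visit in 4.19.1. The Table of Assessments marks it from V1 to V19, but not at V0.

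**The concern.** A form that takes only related events applies the causality judgement as a condition of entry. A form that takes all events records that judgement as data. With the first, the count in each arm is the true count multiplied by the share judged related. That share is unknown and cannot be estimated afterwards, because the excluded events are not on the form.

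Comparing safety and tolerability between doses is a stated aim, and the Fisher comparison is part of how it is addressed. It is least reliable for events that nobody expected, since these are the ones least likely to be attributed to the laser. Events left off the form may not be recoverable later.

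The narrow reading is one that site staff could reasonably adopt. The missing mark at V0 fits it: a form for laser-related events has nothing to record before the first session, whereas 4.17.1 starts recording at consent.

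**Working it through.** **Texts side by side.**

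- Scope: 4.10 takes events related to the application of TLT. The word *only* is not in the text, but it is the fair reading. Sections 4.17.1 and 4.17.3 take all events.
- Start: 4.17.1 starts at consent. The Table of Assessments has no mark for the form at V0.
- Relationship: 4.17.3 grades it after recording, from None to Definitive. On a related-only form the grade None would be empty.
- Analysis: 5.5 C and 5.6 use adverse events without restriction, which presupposes that unrelated events are on record.

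**What a filter would do.** The protocol gives no event rates and no figure to reproduce, so the rates below are assumptions. The only input from the protocol is 28 participants per group (5.3). One active arm is compared with sham, and each participant either has a recorded event or does not.

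Recorded rate = true rate × share judged related.

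Chance of a significant result = the sum, over all outcomes (a, s), of Bin(a; 28, recorded active rate) × Bin(s; 28, recorded sham rate), counting outcomes with two-sided Fisher p < 0.05 and the higher rate in the active arm.

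| True rate, active v sham | Share judged related, active v sham | Recorded rate | Chance of a significant excess in the active arm |
|---|---|---|---|
| 40% v 40% | all recorded | 40% v 40% | 1.3% |
| 40% v 40% | 50% v 50% | 20% v 20% | 1.0% |
| 60% v 30% | all recorded | 60% v 30% | 51% |
| 60% v 30% | 50% v 50% | 30% v 15% | 17% |
| 60% v 30% | 25% v 25% | 15% v 7.5% | 4.4% |
| 40% v 40% | 50% v 10% | 20% v 4% | 25% |

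For the fourth row, 0.60 × 0.50 = 0.30 and 0.30 × 0.50 = 0.15, so the difference halves from 30 to 15 points. In the fifth row it is 0.15 − 0.075 = 7.5 points.

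Rows 2, 4 and 5 represent attribution by someone who does not know the arm, with one share applied to every event. That filter creates no false difference, but it hides a real one. If blinded raters recognise typical device effects, such as erythema at the application site, those events are kept more often and the loss is smaller for them than for unexpected events. Row 6 represents attribution that depends on the arm. Only there does a false excess appear.

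**The case against.** The strongest defence is that 4.10 is one descriptive line and 4.17 is the operative text. Section 4.17.3 sends all events to the source document and the CRF without naming the form, and nothing says that the form is the only route into the Fisher test. SAFTEE-SI is self-reported, has no relationship filter, is scheduled at every visit and has its own between-arm analysis in 5.5 C. This stands as far as it goes: loss of events is possible, not certain. It does not remove the conflict, because the scheduled adverse event form is the one that 4.10 defines, and SAFTEE-SI does not supply the adverse event counts.

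A reader might infer two stronger conclusions. The documents support neither.

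*That the safety comparison is biased against the active arms.* The reasoning would be that events under sham are rarely attributed to the laser, and that 5.1 says device operators know the assignment. But 4.11 and 5.1 blind investigators, doctors, patients and outcome assessors. No section has the operator complete the form or judge relationship, and 4.17.3 refers to the investigator's judgement. Section 6.5 does let the principal investigator apply the treatment. Whether the operator is blinded is itself inconsistent (3.2 against section 1 and 5.1), but that is a separate matter and does not show this bias. A filter also removes events from the active arm. Suppose 8 of 28 in each arm truly have an event, 4 are recorded in the active arm, and 2, 1 or 0 under sham. Fisher's test then gives p = 0.67, 0.35 or 0.11.

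*That unrelated serious events would be missed.* Sections 4.17.2 and 6.4.1 require all serious events to go to the DSMB regardless of relationship. Section 4.17.4 adds reporting to the ethics committee and the national authority, and 4.17.5 covers all deaths.

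**Conclusion.** The point holds as an internal inconsistency. Section 4.10 gives the Adverse Event Form a narrower scope than 4.17.1 and 4.17.3 require and than 5.5 C and 5.6 presuppose. If 4.10 is applied, the non-serious event counts depend on a prior causality judgement.

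The direction of bias is uncertain. Under blinded attribution the likelier harm is a masked difference: in the illustration, power falls from about 51% to 17% or to about 4%. Under attribution that depends on the arm, a false excess could appear in about 25% of trials, against 1.3% with full recording. These sizes rest entirely on the assumed event rates and shares and on 28 per arm. They show mechanism and scale and are not predictions. The contradiction itself rests on no assumption. It should be corrected, because the remedy is simple and omitted events may not be recoverable.

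**What to change.** - In 4.10, delete the closing qualifier that ties the form to TLT-related events. State that the form records all adverse events from informed consent, whatever their relationship, with relationship graded as an attribute under 4.17.3. The form's stated use in decisions on continuing can stay as it is.
- In the Table of Assessments, mark the form at V0 so that it matches the start of recording in 4.17.1.
- Check that the heading and instructions on the CRF page carry no relationship restriction.
- In 5.5 C, state that the between-arm comparison uses all adverse events, with related events as a secondary summary.
- If enrolment has begun, ask each site which rule it has followed, and check completed forms against source documents.

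The cost is a sentence in each of two sections, one table mark and a CRF check. No sample size, visit or clinical rule changes.
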